Bonifati 	10	RCT; targeting dyskinesias	No change	Improved	No change
Kleedorfer 	5	Open-label; targeting dyskinesias	"heightened degree of relaxation and tranquility"	Improved	Worsened at ≤60 mg/day

Buspirone is FDA-approved for treatment of generalized anxiety disorder in the general population. Given the heterogeneous phenomenology of anxiety in PD, this study will not be limited to those with generalized anxiety disorder. As there is no intention to use the results of the proposed study to support a new indication, change

in labeling, or change in advertisement for buspirone, the proposed route of administration and dosage are consistent with current prescribing guidelines, and any special safety concerns relate only to potential worsening of PD motor function it is our determination that the proposed study is exempt from the investigational new drug requirements.

## 2. STUDY DESIGN

### 2.1. Overview

This is a single-center, placebo-controlled, double-blind, futility study with participants with PD and anxiety randomized in a 4:1 allocation to flexible dosage buspirone or placebo for 12 weeks. The initial dose will be 7.5 mg twice daily and investigators will increase the dosage as necessary and tolerated up to 30 mg twice daily to achieve the optimal dosage (the dosage with optimal balance of anxiolytic effect and adverse events). Investigators will be encouraged to increase the dosage at two-week intervals until Hamilton Anxiety Scale (HAM-A) is  $\leq 7$  or there has been a 50% reduction in baseline score. The investigator will be allowed to not escalate or decrease the dosage if the participant has significant adverse events. Adverse events, severity of anxiety, presence of dyskinesias, and PD motor function will be assessed at baseline, week 2, 4, 8, and 12. There will be interim telephone visits to assess efficacy and tolerability at week 6 and 10. The primary outcome is the proportion of participants who fail to complete the 12-week study on study drug (any dosage). Secondary analysis of efficacy will focus on the change in outcome variables from baseline to 12 weeks.

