## 1. PURPOSE OF THE STUDY AND BACKGROUND

### 1.1. Purpose of the study

Anxiety is common in patients with Parkinson's disease (PD) and negatively impacts quality of life. Despite this, anxiety is under-treated and there have been no clinical trials specifically examining the pharmacological treatment of anxiety in PD. Buspirone may be effective for the treatment of anxiety in PD. While it has the additional potential benefit of reducing levodopa-induced dyskinesias there have also been concerns that it may worsen PD motor function. The primary objective of this study is to determine the tolerability of buspirone for the treatment of anxiety in Parkinson's disease (PD).

Primary Objective:

To determine the tolerability of buspirone in PD as defined by the proportion of participants who complete the 12-week study on study drug.

Secondary Objectives:

- a. To explore the preliminary efficacy of buspirone in reducing symptoms of anxiety.
- b. To explore the preliminary efficacy of buspirone in reducing levodopa-induced dyskinesias.
- c. To pilot the Parkinson Anxiety Scale (PAS) for assessing change in symptoms of anxiety over time.

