### 2.2. Rationale for Study Design

The primary objective of this study is to determine the tolerability of buspirone in PD. The primary outcome is the proportion of participants who fail to complete the 12-week study on study drug. We hypothesize that  $> 20\%$  of participants will fail to complete the study on study drug. As the primary tolerability concern with buspirone that is specific to the PD population is worsening of motor function, we considered selecting mean MDS-UPDRS motor scale change from baseline to 12 weeks as the primary outcome for tolerability. This approach was rejected as it would not capture alternative reasons for intolerability (such as nausea, headache, or dizziness). The 12-week duration should provide adequate time for response to treatment and to assess any effect on PD motor function.

From the standpoint of sample size calculations and statistical analysis this is a single-arm futility design; a placebo arm is introduced to allow for blinding and calibration. The use of a futility design over a traditional design allows for higher sensitivity at the cost of lower specificity. In other words, the futility design increases the probability of declaring a truly tolerable drug tolerable (correctly failing to reject the null hypothesis of tolerability) at the cost of a decreased probability of declaring a truly intolerable drug intolerable (correctly rejecting the null hypothesis of tolerability). Given the importance of moving a therapeutic for anxiety through and as the expected intolerabilities (headache, nausea, drowsiness, dizziness, and worsening of PD motor function) are either not expected to be serious or expected to be reversible, and could be confirmed in larger studies, this is a favorable scenario.

The secondary exploratory objectives examining the efficacy of buspirone in reducing symptoms of anxiety and in reducing levodopa-induced dyskinesias were included to provide the opportunity to detect a signal of efficacy regarding potential therapeutic uses of buspirone in PD.

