### 2.4 Rationale for Placebo Arm

The introduction of a placebo arm enables the blinding of participants and investigators to treatment. The introduction of some uncertainty regarding treatment assignment for both the participants and investigators will allow for more rigorous assessment of the tolerability of the study drug by reducing bias. The use of a placebo arm will also allow for calibration, to verify assumptions about the background rate of intolerability. The assumed intolerability rate of placebo is zero and the incorporation of a small placebo group allows for verification of this assumption. The study will not be powered for direct between group comparisons. A similar approach has been used in prior PD research studies; in these studies, a placebo group was introduced to verify historical data regarding the anticipated progression of PD (as measured by the Unified Parkinson's Disease Rating Scale), which was used for sample size calculations.

In both cases, the rate of progression in the placebo group did not align with historical data and the researchers were able to perform additional analyses based on an updated rate of progression.

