### 13.2 Planned Statistical Analysis

The primary outcome for tolerability is the proportion of participants who fail to complete the 12-week study on study drug, as described in **Sample Size and Accrual**. The number of participants who fail to complete the study on study drug will be determined and if 7 or more participants fail to tolerate the study drug, the null hypothesis will be rejected. Participants who do not complete the study on study drug for any reason will be considered as experiencing intolerability for purposes of the primary analysis.

As a secondary analysis we will calculate the number of participants who fail to complete the study on study drug due to adverse events; separating them from those who fail to complete the study on study drug for alternative reasons. We will also calculate the number of participants who required dosage reductions during the study and use descriptive statistics to describe the average study drug dosage and dosage reductions.

Safety analyses will include tabulating adverse events by treatment group and severity and codifying the relationship to study drug. Serious adverse events attributable to buspirone treatment will be described in detail. Adverse event incidence will be summarized along with the corresponding 95% two-sided confidence interval. The mean change in MDS-UPDRS motor score and from baseline to 12 weeks will be calculated. We will use descriptive statistics to characterize the range and variability of study drug dosages.

Secondary outcomes related to anxiety will include the mean change in HAM-A score from baseline to 12 weeks, mean change in HADS score from baseline to 12 weeks and the proportion of participants "much improved" or "very much improved" on CGI-I, proportion "much improved" or "very much improved" on PGI-I, and proportion of responders ( $> 50\%$  reduction from baseline or reduction to  $\leq 7$  in HAM-A) at 12 weeks. The secondary outcome regarding levodopa-induced dyskinesias will be the mean change in UDysRS score from baseline to 12 weeks. Similar analyses will be done for all outcomes at 2 weeks, 4 weeks, and 8 weeks. For participants lost to follow up, the

last observation carried forward will be used. We will also correlate mean change in the Parkinson Anxiety Scale scores with mean change in the CGI-I and PGI-I scores.

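### Preliminary efficacy is planned as change from baseline with no buspirone-minus-placebo estimate, so the planned summary cannot isolate a drug signal

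*Combined protocol and SAP*

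**What the plan says.** The secondary objective in section 1.1 is "To explore the preliminary efficacy of buspirone in reducing symptoms of anxiety", with a parallel objective for dyskinesia. Section 2.2 says these objectives were included "to provide the opportunity to detect a signal of efficacy regarding potential therapeutic uses of buspirone in PD".

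On analysis, section 2.1 says "Secondary analysis of efficacy will focus on the change in outcome variables from baseline to 12 weeks". Section 13.2, the only statistical text on efficacy, begins "Secondary outcomes related to anxiety will include the mean change in HAM-A score from baseline to 12 weeks". It goes on to HADS and UDysRS changes, HAM-A responders, and the CGI-I and PGI-I proportions, with last observation carried forward (LOCF) for participants lost to follow-up. It names no model, covariate, between-arm difference or confidence interval for any of these. Treatment group is mentioned in that section only for adverse events.

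Section 2.2 describes the framework: "From the standpoint of sample size calculations and statistical analysis this is a single-arm futility design", and "a placebo arm is introduced to allow for blinding and calibration". Section 2.4 shows that calibration refers to tolerability ("The assumed intolerability rate of placebo is zero") and adds "The study will not be powered for direct between group comparisons".

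**The concern.** Anxiety scores can improve over 12 weeks without any drug effect. Participants enter with a PAS score of at least 14. They are contacted every two weeks, their dosage is adjusted according to HAM-A, and they may continue existing anxiolytics, antidepressants and psychotherapy. An investigator rates HAM-A. Improvement common to both arms is therefore plausible, and change within one arm cannot separate it from a drug effect.

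The protocol makes this argument itself in another context. Section 2.4 cites two earlier Parkinson's disease studies in which the placebo group did not behave as historical data predicted, and uses them to justify a concurrent control for the tolerability assumption. The same reasoning applies to efficacy.

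At stake is whether the secondary objective can be answered. If only changes from baseline are reported, a later efficacy trial may be planned on a figure that includes placebo response and natural improvement. The control data that would remove this in expectation are already collected under the schedule of activities.

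**Working it through.** **Plan's own figures.** The documents give no sample size or power for efficacy. The tolerability calculation supplies the arm sizes. An exact binomial rule of 7 or more failures among 21 has power 0.7998 at a true rate of 40%, which matches the stated 80%. At 4:1, 21 × 5/4 = 26.25, so 27 in total. Conversely, 27 × 4/5 = 21.6, so the arms would be 21 v 6 or 22 v 5. The synopsis and section 4.1 give 35 participants, and 35 × 4/5 = 28, so 28 v 7. Section 3.1 says the 35 includes screen failures, so 28 v 7 is an upper case.

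**Precision of an unadjusted contrast**, in SDs of change. Half-width = t(0.975, n1+n2−2) × √(1/n1 + 1/n2).
- 21 v 6: 2.06 × 0.463 = 0.95
- 22 v 5: 2.06 × 0.495 = 1.02
- 28 v 7: 2.03 × 0.423 = 0.86

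**Effect of baseline adjustment.** Let r be the correlation between baseline and week 12; the documents give none, so 0.3, 0.5 and 0.7 are assumed. The large-sample ratio of the adjusted half-width to the change-score half-width is √((1+r)/2) = 0.806, 0.866, 0.922. At N = 27 two small penalties apply:
- chance baseline imbalance: √(1 + 1/(N−4)) = √(1 + 1/23) = 1.0215
- one lost degree of freedom: t(24)/t(25) = 2.064/2.060 = 1.002

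Their product is 1.024. The ratios become 0.825, 0.887 and 0.944, a narrowing of about 17%, 11% and 6%. At 21 v 6 the adjusted half-width is then about 0.79, 0.85 and 0.90 SD of change.

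**Proportions.** At an assumed rate of 50% in both arms, the normal-approximation half-width is 1.96 × 0.5 × 0.463 = 0.45 at 21 v 6 and 1.96 × 0.5 × 0.423 = 0.41 at 28 v 7. These are rough figures at such counts.

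**Illustration of the ambiguity.** Suppose buspirone had no effect and everyone improved by a shared 0.3, 0.5 or 0.8 SD of change (assumed). A two-sided 5% paired test in 21 buspirone participants, with noncentrality shift × √21, would be significant with probability 26%, 59% or 94%. The plan specifies no such test; this shows only how readily shared improvement can look like a signal.

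**Where regression to the mean applies.** Selection is on the PAS at screening, and the PAS is repeated at baseline. HAM-A and HADS were not selection measures, so the effect reaches them only in part, through their correlation with the PAS. No entry criterion concerns dyskinesia or motor severity, so the argument does not extend to UDysRS or MDS-UPDRS motor.

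**The case against.** The strongest reply is that efficacy here is exploratory. It has no test, threshold or go/no-go rule; the only decision rule concerns tolerability; and section 2.4 openly says the study is not powered for comparison between arms. That stands as a reason not to test. It does not explain the absence of an estimate with an interval when randomised controls are measured on the same scales.

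A second reply is that sections 2.1 and 13.2 merely name outcome variables, and that reporting by arm is implied in a randomised, placebo-controlled trial. This has some force. A reader might infer that the plan will analyse the buspirone arm alone and credit its whole change to the drug, so that the signal is overstated by the full placebo response. The documents do not say that. What they show is silence on any contrast, alongside single-arm wording that section 2.2 uses mainly to explain the tolerability design. Arm means alone would still leave the difference and its uncertainty unstated.

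Third, with complete data a simple difference in mean change is also unbiased under randomisation. Choosing baseline adjustment is a matter of precision, and the gain at this size is modest. That is correct: the contrast is the main omission, and adjustment is secondary.

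**Conclusion.** The point holds as a gap in the analysis plan. As written, the efficacy summary cannot separate a drug effect from placebo response and natural improvement, or, for the anxiety scales only, from partial regression to the mean. The stated aim of finding a signal of efficacy is therefore not met. The primary tolerability outcome is unaffected.

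The size of the mixture cannot be derived from the documents. The contrast would be imprecise: about ±0.86 to ±1.02 SD of change unadjusted, depending on arm sizes, and somewhat narrower with adjustment under the assumed correlations.

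A reader might also infer that the between-arm estimate would be free of bias. The documents do not support that: section 13.2 uses LOCF for participants lost to follow-up, and this may bias the difference if dropout differs by arm.

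**What to change.** In section 13.2:
- Report every efficacy outcome by arm.
- For HAM-A, HADS anxiety and UDysRS, give the buspirone-minus-placebo difference at week 12 adjusted for the baseline value, with a 95% CI, labelled exploratory estimation without a test. The section currently names HADS without a subscale, so state that the anxiety subscale is meant.
- For HAM-A responders, CGI-I and PGI-I, give the between-arm difference in proportions with a 95% CI from a method suited to small counts. CGI-I and PGI-I have no baseline value to adjust for.
- Report MDS-UPDRS motor by arm with the same baseline-adjusted difference and CI, but as a safety outcome.
- State that any efficacy signal will be described from these contrasts, not from change within an arm, and that LOCF may bias them if dropout differs by arm.

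The cost is a few sentences, best added before unblinding, and minor analysis of data already collected. No visits or participants are added. The downside is wide intervals, and for UDysRS the contrast may say little, since dyskinesia is not an entry requirement.

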### 2.2. Rationale for Study Design

The primary objective of this study is to determine the tolerability of buspirone in PD. The primary outcome is the proportion of participants who fail to complete the 12-week study on study drug. We hypothesize that  $> 20\%$  of participants will fail to complete the study on study drug. As the primary tolerability concern with buspirone that is specific to the PD population is worsening of motor function, we considered selecting mean MDS-UPDRS motor scale change from baseline to 12 weeks as the primary outcome for tolerability. This approach was rejected as it would not capture alternative reasons for intolerability (such as nausea, headache, or dizziness). The 12-week duration should provide adequate time for response to treatment and to assess any effect on PD motor function.

From the standpoint of sample size calculations and statistical analysis this is a single-arm futility design; a placebo arm is introduced to allow for blinding and calibration. The use of a futility design over a traditional design allows for higher sensitivity at the cost of lower specificity. In other words, the futility design increases the probability of declaring a truly tolerable drug tolerable (correctly failing to reject the null hypothesis of tolerability) at the cost of a decreased probability of declaring a truly intolerable drug intolerable (correctly rejecting the null hypothesis of tolerability). Given the importance of moving a therapeutic for anxiety through and as the expected intolerabilities (headache, nausea, drowsiness, dizziness, and worsening of PD motor function) are either not expected to be serious or expected to be reversible, and could be confirmed in larger studies, this is a favorable scenario.

The secondary exploratory objectives examining the efficacy of buspirone in reducing symptoms of anxiety and in reducing levodopa-induced dyskinesias were included to provide the opportunity to detect a signal of efficacy regarding potential therapeutic uses of buspirone in PD.

This clinical trial will also pilot the use of the recently developed and validated Parkinson Anxiety Scale, which adequately captures the full phenomenological spectrum of anxiety in PD, for detecting change over time and determine the feasibility of using it in larger phase III trials. We selected a cut-off of  $\geq 14$  on the Parkinson Anxiety Scale as necessary for study eligibility, consistent with the data from the initial validation study. We considered the use of a more traditional scale, such as the Hamilton Anxiety Scale or Hospital Anxiety and Depression Scale for use in the inclusion criteria, however concluded that these scales would not capture all of the subtypes of anxiety that are seen in PD and would result in the exclusion of appropriate participants.

### 2.3. Rationale for Dosage

A flexible dosage design was selected to reflect clinical practice, render more generalizable results, and remain consistent with general prescribing guidelines. As such, this study assesses the tolerability of buspirone rather than the tolerability of a specific dosage of buspirone. To minimize the risk for investigator bias influencing dosage adjustments we will employ specific parameters for dosage adjustment. Participants will receive 7.5 mg of buspirone or placebo twice daily for the first two weeks. Increases can be made at two-week intervals if a dosage is without significant adverse events and optimal anxiolytic effect (defined as Hamilton Anxiety Scale score  $<50\%$  of baseline score or  $\leq 7$ ) has not been attained. These are traditional parameters used to define treatment efficacy in studies of anxiolytic medications. Pre-specified dosage levels of 7.5 mg twice daily, 10 mg twice daily, 15 mg twice daily (with 3 preceding days of 12.5 mg twice daily), 20 mg twice daily (with 3 preceding days of 17.5 mg twice daily), 25 mg twice daily (with 3 preceding days of 22.5 mg twice daily), and 30 mg twice daily (with 3 preceding days of 27.5 mg twice daily) will be imposed to minimize dosage variation and maintain consistency with prescribing guidelines. This is detailed in section 5.1.2. We anticipate that future phase III efficacy trials would employ a similar design.

### 2.4 Rationale for Placebo Arm

The introduction of a placebo arm enables the blinding of participants and investigators to treatment. The introduction of some uncertainty regarding treatment assignment for both the participants and investigators will allow for more rigorous assessment of the tolerability of the study drug by reducing bias. The use of a placebo arm will also allow for calibration, to verify assumptions about the background rate of intolerability. The assumed intolerability rate of placebo is zero and the incorporation of a small placebo group allows for verification of this assumption. The study will not be powered for direct between group comparisons. A similar approach has been used in prior PD research studies; in these studies, a placebo group was introduced to verify historical data regarding the anticipated progression of PD (as measured by the Unified Parkinson's Disease Rating Scale), which was used for sample size calculations.

In both cases, the rate of progression in the placebo group did not align with historical data and the researchers were able to perform additional analyses based on an updated rate of progression.

We recognize the potential for anxiety to not improve or worsen, particularly among those participants in the placebo arm, and that this may have a negative effect on their quality of life. However, we believe that the benefits of including a placebo arm for blinding and to allow for calibration of baseline assumptions regarding intolerability outweigh the potential risks. We will institute measures to ensure the safety of all participants. Of note, participants will not be asked to discontinue any pre-existing anxiolytics or antidepressants (with the exception of MAO inhibitors which pose a potential safety concern) or discontinue psychotherapy to participate in the study. Participants will only be asked not to increase the dosage of pre-existing anxiolytics or antidepressants, start new anxiolytics or antidepressants, or initiate psychotherapy for the duration of the study. Investigators will exclude from participation any patients where there is a concern for patient safety. If a participant's anxiety symptoms worsen significantly during the course of the study or if he/she develops suicidal ideation, which is deemed severe enough to reflect a significant suicidal risk, we will terminate the participant from the study and we will immediately refer the patient to a mental health provider for treatment. The investigator will determine the most appropriate referral, which may be referral to an outpatient mental health provider or referral to the Comprehensive Psychiatric Emergency Program. Participants and their caregivers will be encouraged to contact the investigators at any time if there is concern about worsening anxiety or adverse experiences.

